7.2.1.2 Hair reduction assessment

Hair counts will be accomplished by analysis of photographs. The original image of the photographs will be saved and archived in its original form by the site and a copy will be sent to the sponsor. The image will be enlarged to a uniform size to facilitate counting and the file shall be saved (locked) into a PDF format.

At baseline, immediately before treatment 3 and 6, 1M FU1, 3M FU2 and 6M FU3, a copy of the image shall be printed. Each image will be reviewed by the investigator or his/her designees. Additional copies of baseline, 1M FU1, 3M FU2 and 6M FU3 will be sent to two other reviewers who are blinded to the treatments. The reviewer will mark each hair identified with a red pen, and each of these marks will be tallied to obtain hair count. For a detailed hair count explanation please refer to section 7.4.2.2.

7.2.2 Subject Subjective Assessments

7.2.2.1 Level of comfort

Treatment associated level of comfort experienced by the subjects will be measured on a 10cm Visual Analogue Scale (VAS) were 0 cm is 'no pain' and 10 cm is 'intolerable pain'. The subjects will be given a VAS and be asked to mark their perception of pain immediately following each treatment.

7.2.2.2 Level of improvement and satisfaction

Subject's Improvement and Satisfaction with treatment will be recorded by a 5-point Scale: 1=None; 2=Slight; 3=Moderate; 4=Good; 5=Very Good.

Table 1– Clinical Evaluation Tools

Claim/task	When to conduct?	Tool
Photography	Baseline, immediately before treatments 3, 6, 1M±7D FU1, 3M±7D FU2 and 6M±7D FU 3	Standardized digital photographs
Hair count by single study personnel	Baseline, immediately before treatments 3, 6, 1M±7D FU1, 3M±7D FU2 and 6M ±7D FU3	Standardized digital photographs
Hair count by blinded reviewers	Baseline, 1M ±7D FU1, 3M ±7D FU2 and 6M ±7D FU3	Standardized digital photographs
Immediate and short term response	Immediately following treatments 1-6	Examination of skin in the treated area based on 5 level scale
Subjects comfort assessment	Immediately following treatments 1-6	VAS
Subjects improvement/satisfaction assessment	Treatments 3, 6, 1M ±7D FU1, 3M ±7D FU2 and 6M ±7D FU3.	5 point scale
Safety	Throughout study	Examination of skin in the treated area, interview subjects

7.3 Screening Procedures

7.3.1 Subject Enrollment

If the subject has met the preliminary study criteria the study doctor, and/or his designee, will obtain an informed consent from the subject, clearly indicating his/her understanding of the requirements and possible risks involved with study participation and other applicable treatment options.

During the first visit, the study investigator, and/or his designee, will screen the subject for eligibility to participate in the clinical study using the Inclusion, Exclusion criteria. During screening the study doctor will review the subject's medical history, and examine the subject's targeted area to ensure that it meets the study criteria. The subject will complete screening and the treatment will be scheduled. Treatment may be performed on the day the subject was enrolled or no later than one week following enrollment and screening.

During the first visit, the investigator will ask women of child-bearing potential for the date of their last period, if not applicable the investigator shall inquire about the form of contraceptive they use to confirm they meet the inclusion criteria.

7.3.2 Subject Identification

At enrollment each subject will receive a unique identifying number that will be composed of a consecutive number and his/her initials. This unique identifier will be used throughout the entire study and will be entered in the subject's CRF for each treatment and photographs.

7.4 Pre-Treatment Procedures

7.4.1 Subject Skin care and medication

- Subjects will be instructed to avoid sun exposure for at least four weeks before treatment and to use broad spectrum sunscreen of no less than 30 SPF on a daily basis, replenishing it as often as needed throughout the course of the study. In addition Tanning is to be strictly avoided.
- Subjects should not pluck, tweeze, wax, use depilatory creams, electrolysis, hair bleaching agents, hair growth inhibitors (such as Vaniqa®) or any treatment with a laser or other devices in the study treatment throughout the course of this study and follow-up examinations.
- Immediately before treatment, the area will be shaved to the skin surface using foam or gel to minimize skin irritation.

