Main Inclusion Criteria	
 • Healthy adults, females or males older than 21 years of age with skin type V-VI; hair color Black or dark brown; having a suitable treatment area for hair removal. Two small anatomical areas (right and left axillae and double sided bikini line) or; • One double sided large area (right and left thighs)or; • One large area (whole back / abdomen) 
Other areas not defined above, as face, are not allowed to be treated.
	
Main Skin Related Exclusion Criteria	
 • Active infections in the treatment area. • Dysplastic nevi in the treatment area. • Tattoos in the treatment area. • Significant concurrent skin conditions or any inflammatory skin conditions in the treatment area. • Active cold sores, open lacerations or abrasions in the treatment area. • Chronic or cutaneous viral, fungal, or bacterial diseases. • Deep suntan, recent suntan, sunburn or artificially tanned skin. • Current skin cancer. • History of skin cancer or pre-cancerous lesions at the treatment areas. 	

Investigational Treatment and Study Duration	Each subject will receive six treatments at four to six weeks intervals and return for follow-up visits at one (\pm seven days), three (\pm seven days) and six (\pm seven days) months after the last treatment for evaluation of the treated areas.
Criteria for Evaluation	
Primary endpoints
 
 • Hair count reduction from photographs 3 months following the last treatment - FU2, as compared to baseline (hair removal) • Hair count reduction from photographs 6 months following the last treatment - FU3, as compared to baseline (permanent hair reduction) 
Secondary endpoints
 
 • Hair count reduction from photographs 1 month following the last Treatment - FU1 • Subject's assessment of comfort associated with treatments using a VAS scale, following each of the 6 treatments. • Subject's satisfaction with hair removal treatments and assessment of improvement using a five point scale, at visit 3, 6, 7, 8 & 9. • Immediate response following each treatment, defined as type and intensity of response and the time it takes for it to subside. Should be removed any adverse events associated with various setting used during the treatment and follow-up period.

Table of Contents

1	Introduction.....	8
1.1	Background.....	8
1.2	Rationale for Evaluation	8
2	Study Design.....	9
3	Study Objectives.....	9

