5.2 Eligibility

Each subject will be evaluated by the Investigator to assess his/ her suitability for entry into this study according to the following criteria:

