5.2.1 Inclusion Criteria

Subjects must meet all of the following inclusion criteria to be entered into the study:

1. Able to read, understand and provide written Informed Consent;
2. Subject has black or dark brown terminal hairs in the areas to be treated.
3. Terminal hair density requirement of greater than 15 hairs within the hair count site (3x3 cm area) as determined by manual hair count performed by the study investigator.
4. Healthy adult, male or female, 21 years of age or older with skin type V-VI;
5. Having a suitable treatment area for hair removal;
6. Able and willing to comply with the treatment/follow-up schedule and requirements;
7. Women of child-bearing potential (women who have not had a hysterectomy, bilateral oophorectomy or are not postmenopausal) are required to be using a reliable method of birth control at least three months prior to enrollment and throughout the course of the study.

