5.2.2 Exclusion Criteria

Any of the following will exclude the subject from the study:

1. Subject has light, gray terminal or fine hairs in all/some parts of the treated area;
2. Pregnant, expectation of pregnancy, postpartum or nursing (<6 months);
3. Hormonal disorders that may affect hair growth;
4. Immunosuppressive diseases, including AIDS and HIV infection, or use of immunosuppressive medications;
5. Livedo reticularis;
6. Uncontrolled systemic diseases such as diabetes;
7. Active infections in the treated area;
8. Dysplastic nevi;
9. Significant concurrent skin conditions or any inflammatory skin conditions;
10. Active cold sores, open lacerations or abrasions;
11. Chronic or cutaneous viral, fungal, or bacterial diseases;
12. Current cancer;
13. History of skin cancer or pre-cancerous lesions at the treatment areas;
14. Use of Accutane™ (Isotretinoin) within the past six month;
15. Keloid or Hypertrophic scar formation in the treatment area;
16. Tattoos in the treatment area;
17. Bleeding coagulopathies or use of anticoagulants;
18. Auto-immune disorders;
19. Erythema abigne, when identified treatments should be discontinued;
20. Photosensitivity disorder that can be exacerbated by laser or intense light;
21. Herpes simplex in the treatment area;
22. Use of medications, herbal supplements, perfumes or cosmetics that may affect sensitivity to light;
23. Poor wound healing;
24. Sunburns;
25. Unable or unlikely to refrain from artificial tanning, including the use of tanning booths, prior (at least a month) and during the course of the evaluation;
26. Prior skin treatment with laser or other devices on the same treated areas within the last six months prior to study enrollment or during the course of the study.

6 Materials

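### The synopsis bars deep or recent suntan but the section 5.2.2 exclusion list omits it, and no visible screening step asks about sun exposure before treatment 1

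*Combined protocol and SAP*

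**What the plan says.** The synopsis, under its main skin-related exclusions, bars "Deep suntan, recent suntan, sunburn or artificially tanned skin".

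Section 5.2 has the investigator judge "suitability for entry into this study according to the following criteria", and the lists in 5.2.1 and 5.2.2 follow directly. In 5.2.2, item 24 is sunburn. Item 25 begins "Unable or unlikely to refrain from artificial tanning, including the use of tanning booths, prior (at least a month" and extends through the evaluation itself. None of the 26 items names a natural suntan.

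On sun exposure before treatment, section 7.4.1 says: "Subjects will be instructed to avoid sun exposure for at least four weeks before treatment". The same bullet asks for daily sunscreen of at least SPF 30 and tells subjects not to tan. These are instructions to subjects, not entry criteria.

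On timing, section 7.3.1 says: "Treatment may be performed on the day the subject was enrolled or no later than one week following enrollment and screening". Appendix I agrees, and allows Visit 0 and Visit 1 to be merged. Screening in 7.3.1 consists of the criteria, a medical history, an examination of the target area, and a question on last period or contraception. No question on sun exposure appears there or in Appendix I.

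**The concern.** A synopsis of main criteria should be a subset of the full list. Here it holds an exclusion that the full list lacks, and the full list is the one that sites are directed to use. With 20 planned sites, some may screen from one text and some from the other.

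The omission bears on safety, which is the first primary objective (section 3.1). Section 1.2 explains that melanin elsewhere in the skin competes with the follicle for the light, and that darker skin is therefore harder to treat. Section 9.1.6 lists blistering, burns and PIH among the anticipated adverse events. The sponsor judged suntan worth excluding, and the operative list does not carry that judgement through.

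The timing issue compounds it. An instruction governs only the days after it is given. If it comes at enrolment, most of the four weeks before treatment 1 have already passed, and only a question about the past could show whether they were sun-free.

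**Working it through.** The plan gives no figure to reproduce. The check is a comparison of texts and a count of days.

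**Step 1: the two exclusion texts.**

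| Skin state | Synopsis | Section 5.2.2 |
|---|---|---|
| Sunburn | barred | barred (item 24) |
| Artificial tan | barred | addressed through behaviour, with a look-back of at least a month (item 25) |
| Deep natural suntan | barred | no item |
| Recent natural suntan | barred | no item |

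Item 9 of 5.2.2 (significant concurrent or inflammatory skin conditions) might be stretched to cover a tan. But the synopsis lists skin conditions and suntan as separate exclusions, so the sponsor did not treat one as including the other.

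**Step 2: the four weeks before treatment 1.**

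Inputs:
- sun avoidance required: 4 weeks = 28 days (7.4.1)
- enrolment to treatment 1: 0 to 7 days (7.3.1, Appendix I)
- assumption, not stated in the documents: the instruction is first given at Visit 0

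Days covered by the instruction = interval from Visit 0 to treatment 1:
- same-day treatment: 0/28 = 0%
- treatment at day 7: 7/28 = 25%

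Days that come before the instruction: 28 − 7 = 21 to 28 − 0 = 28, which is 75% to 100% of the period. This measures when the instruction is given. It does not measure how much sun any subject had.

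**Step 3: treatments 2 to 6.** The interval between treatments is 4 to 6 weeks, or 28 to 42 days. Since 28 ≥ 28, an instruction given at Visit 0 covers the full four weeks before each later treatment. The timing gap is confined to treatment 1.

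**Step 4: does another step supply the missing history?**
- The examination under 7.3.1 checks the "targeted area to ensure that it meets the study criteria". The listed criteria contain no suntan item, and an examination cannot date past exposure.
- Inclusion 6, "Able and willing to comply with the treatment/follow-up schedule and requirements", looks forward. Reading it to bar a recently exposed subject needs a history that no visible step collects.
- Where the sponsor wanted a specific question at the first visit, 7.3.1 writes it out (last period, contraception).

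**The case against.** The strongest reply is that the exclusion is already in the protocol. Section 5.2.2 is silent on natural suntan, not contrary to the synopsis, and 7.3.1 refers to the inclusion and exclusion criteria without naming 5.2.2. A site that also applies the synopsis would exclude the subject. This stands, and it limits the claim to what a site working from 5.2.2 could do. A reader might infer that the protocol permits tanned subjects; it does not.

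Second, the 0% to 25% figure depends on the instruction being first given at Visit 0. Section 7.3.1 opens with "If the subject has met the preliminary study criteria", which implies earlier contact, and section 5.1 recruits from the investigator's own patients, so earlier instruction is feasible. This also stands. The figure is conditional, because the documents do not say when the instruction is given. Nor can the absence of a question be proved beyond the visible text, since the case report forms are not reproduced.

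Third, there are safeguards. Section 7.4.3 requires test spots before treatment 1, starting low (5-10 J/cm², 35-50 ms), assessed after at least 2 hours, with no treatment until the reaction is evaluated. They test the skin as it is on the day, which is the relevant hazard, and treatment is confined to axillae, bikini line, thighs, back and abdomen. These steps reduce the risk. They do not remove it: a reading at about two hours cannot show a reaction that 9.1.6 defines by its failure to resolve within 2-3 days.

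Fourth, 7.4.1 pairs sun avoidance with daily sunscreen, which suggests that incidental exposure is expected. A reader might infer that any exposure in the four weeks should bar entry. Neither 7.4.1 nor the synopsis says so.

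**Conclusion.** The point holds as a minor subject-safety and consistency correction, in two parts.

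The eligibility mismatch is certain on the text: 5.2.2 lacks an exclusion that the synopsis contains, and 5.2 points sites to the list without it.

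The timing gap is conditional. Unless the sun-avoidance instruction is given before Visit 0, it cannot take full effect before treatment 1, and no visible step asks about exposure before then.

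Two stronger readings are not supported. The 75% to 100% of days before the instruction is not a share of subjects who were exposed, and the documents give no rate of suntan or prior exposure from which to estimate one. Nor do they support any claim of a higher adverse event rate or of bias in the hair-count comparison.

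**What to change.** 1. Add an exclusion to 5.2.2 for deep or recent suntan in the treatment area, and use the same words in the synopsis.
2. Add one question to 7.3.1, asked at Visit 0 before the baseline photographs: has the treatment area been tanned, or had significant sun exposure, in the previous four weeks? If yes, do not enrol yet and rescreen later.

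Baseline photographs and counts are then taken at the rescreening visit, so the interval from baseline to treatment 1 stays at 0 to 7 days and both primary endpoints are untouched. There is no need for an absolute no-exposure rule, or for deferring treatment 1 beyond the 7-day limit with a second baseline. Either would go further than the safety point requires.

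The cost is amendment wording in the synopsis, 5.2.2 and 7.3.1, with the ethics approval that 10.10 requires, and one history question. Some subjects will be excluded or will start later. If the last significant exposure was d days before Visit 0, the four-week question can be answered no from day 28 − d: day 8 for d = 20, and day 28 at the latest for d = 0, if the subject avoids the sun from then on. The documents do not allow an estimate of how many subjects this would delay.

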7.4.2 Photography and hair count

7.4.2.1 Photography

Photographs are mandatory for this research; they may also be used by the Sponsor (Venus Concept Ltd.) for future educational and marketing purposes.

Photographs will be taken prior to treatment and throughout the study according to specified time points detailed in Table 1, utilizing standard scientific equipment.

The photos should be taken in a private room or area of the clinic under controlled conditions, including the distance, angle, background and lighting in order to achieve high-quality before & after sets. Do not use direct illumination. The subject should be placed in the same position each time. As each photograph is taken, it should be viewed to ensure that it is in focus and is similar to its baseline counterpart in all technical aspects, including lighting, distance and angle.

For consistency purposes, the same person should ideally take all study photographs, especially per subject. The digital files should follow a consistent standard naming scheme, for example: 001TM_Tx1_right axillae.

In each photography session the order of photos should be as follows:

1. First photo is of the whole treatment area including a small sticker with the subject initials and date.
2. A close up photo graph including the hair count sticker template as detailed in the section below.

Effort will be made to ensure subject privacy when taking photographs of the groin/ bikini area. Black uniform undergarment should be used when photographing the treatment area.

7.4.2.2 Hair count

The customized hair count sticker templates detailed in section will be supplied by the sponsor. Templates consist of a rectangular frame sticker with a one square inch rectangular window (25.4mm x 25.4mm). The sticker template will be placed directly on the skin and the hairs in this window will be counted at specific visits during the study as detailed in section 7.2.1.1. For identification, the subject's ID, treatment area and visit date shall be filled out on the designated area upon the template frame.

The following procedure is intended to ensure that the template is placed in the same position during subsequent visits:

7.4.2.2.1 Baseline visit (prior to the 1st treatment):

1. The appropriate treatment area will be decided.
2. The hair in the area to be treated will be scissor trimmed to 2 mm to facilitate hair counts for photography.
3. The template will be completed with the subject ID, treatment area and date.
4. The template will be placed directly on the skin, in the area to be treated.
5. A clear transparency sheet will be placed over the treatment area, over the template.
6. The transparency sheet will be marked with a permanent marker to indicate anatomical landmarks and the sticker template location.
7. A general photograph of the sticker template, overlaid with the transparency sheet will be taken, as well as a close-up picture.
8. The transparency sheet will be removed and an additional close-up picture of the sticker template will be taken for the baseline hair count.

7.4.2.2.2 "Hair count" treatment visits [3, 6, 1M±7D FU1, 3M±7D FU2 and 6M±7D FU 3]:

1. The hair in the area to be treated will be scissor trimmed to 2 mm to facilitate hair counts from photography.
2. The template will be completed with the subject ID, treatment area and date.
3. The sticker template will be placed on the area to be treated using anatomical landmarks and the baseline picture to properly position the transparency sheet prepared in the baseline visit.
4. A close-up photograph of the sticker template will be taken.
5. The sticker will then be removed, the area shaved to the skin surface and treatment performed.

7.4.3 Test spots

Up to 3 test spots will be performed in the selected treatment area to determine the optimal parameters / setting combinations prior to the first treatment and later on in the treatment scheme if any alterations in treatment parameters are needed. It is important to consider all possible treatment parameters (fluence, pulse duration, # of pulses, etc.). It is always recommended to start with a low energy level and observe the skin's reaction before gradually increasing the energy. The Investigator will start the test spot at a low fluence and adjust it upwards based upon the skin response and the subject's feedback. Subjects may feel slight warmth of the skin, or minimal discomfort during treatment, but should not experience significant pain.

Assessment of the test spot will be performed following at least 2 hours. It is important not to start treatment prior to full evaluation of the reaction to the test spot and optimal parameters identified.

Table 2 - Guidelines Test Spot Treatment Parameters

Skin Type	Fluence Set point (J/cm ²)	Pulse Time (ms)	# of Pulses	Notes for next set of Test Spots
V	5-10J/cm ²	35-50 ms	1	If No AE/Pain/clinical endpoint: increase fluence, decrease pulse duration. If AE/Pain does occur: decrease fluence; or increase pulse duration.
VI	5- 10 J/cm ²	35-50 ms	1	If No AE/Pain/clinical endpoint: increase fluence; and/or # of pulses. If AE/Pain does occur: decrease # of pulses; and/or fluence.

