7.5 Treatment

The treatment areas are divided into 3 groups. Each Subjects will be allocated to one of the following groups::

- Two small anatomical areas (right and left axillae and double sided bikini line) or;
- One double sided large area (right and left thighs) or;
- One large area (whole back / abdomen)

Other areas not defined above, as face, are not allowed to be treated.

Each site will recruit four subjects for each one of the three treatment groups (as specified above or in this section)

Based on the mild nature of treatment, anesthesia is not required. Treatment procedure should include positioning of the patient in a manner that enables access to the treated anatomical site. The positioning of subjects during treatment will be contingent on the location of the treated anatomical site.

Before starting treatment apply a layer of conductive gel to the treatment area.

After applying the conductive gel, locate the applicator in close contact, perpendicular to the skin with no pressure applied. Pressing the applicator will fire the IPL pulse. In order to ensure full coverage of the treatment area applicator placement should overlap approximately 1/3 of the previously treated skin.

During whole treatment duration, the safety of the subject and study personnel must be secured via the use of adequate safety eye protection.

During whole treatment duration, subject reaction must be monitored and if the subjects report an intolerable level of pain, treatment shall be ceased immediately. The treatment session will last until the required treated area is covered.

The normal response to these treatments is transient erythema and edema. If any side effects occur, as indicated in the protocol, they will be recorded.

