9.1.6 Anticipated Outcome Related Adverse Events

Anticipated adverse events in this study may include: blistering, burns, excessive edema or erythema (excessive considered as edema or erythema that do not resolve within 2-3 days), infection, PIH and scarring.

Any anticipated AE that occurs at any time during or after the use of the study device must be reported by the Investigator to Venus Concept. If the anticipated AE, in the opinion of Venus Concept or the Investigator, is likely to affect the safety of the subjects or the conduct of the study, the IRB/ Helsinki/ other ethic committee will be notified of the effect within 10 working days after Venus Concept first receives notice of it. In this study if an adverse event of PIH occurs the Investigator will continue following the subject until the PIH is resolved or up to 6 months following the last visit, whichever comes first.

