Appendix I Study Flow Chart

Study Activities	Visit #0*	Visit #1***	Visit #2	Visit #3	Visit #4	Visit #5	Visit #6	Visit #7§	Visit #8§	Visit #9§§
	Pre-Tx	Tx #1 Up to 7 days after Visit 0	Tx #2 4-6 WKS POST Tx1	Tx #3 4-6 WKS POST Tx2	Tx #4 4-6 WKS POST Tx3	Tx#5 -6 WKS POST Tx4	Tx #6 4-6 WKS POST Tx5	FU #1 1M±7 D FU	FU #2 3M±7 D FU	FU #3 6M±7 D FU
Qualify for study: Informed Consent, Eligibility assessment, Demographic information, Medical history & treatment related medical examination	X									
Test spots**		X Pre-Tx								
Photographs	X			X Pre-Tx			X Pre-Tx	X	X	X
Treatment		X	X	X	X	X				
Immediate and short term response		X	X	X	X	X	X			
Hair Count by study personnel	X			X			X	X	X	X
Hair Count by blinded evaluators (to be conducted post study)	X							X	X	X
Subject's comfort assessment		X	X	X	X	X				
Subject's improvement/satisfaction				X			X	X	X	X
Adverse events recording		X	X	X	X	X	X	X	X	X
Study termination										X

* Visit #0 includes various screening activities and explanations to the candidate regarding the evaluation; should the subject sign the Informed Consent Form, complete the test spot procedure and undergo treatment during Visit #0, it will effectively become merged with Visit #1.

** Test spots should be performed prior to Tx #1 and with any treatment parameter alternation later on in treatment regime.

*** An Intermediate Safety report will be performed following Tx #1.

§ A Hair Removal report will be performed following FU #1 and FU #2 of 1M ±7D; 3M ±7D.

§§ A Permanent Hair Reduction report will be performed following FU #3 of 6M±7D.

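### On a same-day start, a test spot read from 2 hours onward cannot show edema or erythema lasting 2-3 days before the whole area is treated

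*Combined protocol and SAP*

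**What the plan says.** Section 7.4.3 provides for up to three test spots in the treatment area before the first treatment, in order to choose the settings. On timing it says "Assessment of the test spot will be performed following at least 2 hours". It adds that treatment should wait until the reaction has been fully evaluated and the settings identified, but gives no duration or criterion for that evaluation.

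Section 7.3.1 says "Treatment may be performed on the day the subject was enrolled or no later than one week following enrollment and screening". In Appendix I the column for the first treatment reads "Tx #1 Up to 7 days after Visit 0", and the test-spot row is marked in that column as a pre-treatment step. One footnote says "Test spots should be performed prior to Tx #1", with no minimum gap. Another covers consent, spot and treatment in a single attendance: should the subject "complete the test spot procedure and undergo treatment during Visit #0, it will effectively become merged with Visit #1".

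Section 7.5 says "The normal response to these treatments is transient erythema and edema" and has each session continue until the required area is covered. Section 9.1.6 lists excessive edema or erythema among the anticipated adverse events, with the definition "excessive considered as edema or erythema that do not resolve within 2-3 days".

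**The concern.** Edema and erythema are expected after treatment, and the protocol tells the harmful form from the normal one by duration alone. A spot read after 2 hours carries no information on duration. If Tx 1 follows the same day, a reaction that looks ordinary at the reading may prove persistent only after the axillae and bikini line, the thighs, or the back or abdomen have been treated at the chosen setting. Table 2 also advises raising the fluence when no adverse event, pain or clinical endpoint is seen, so an unremarkable early reading can lead to a stronger setting.

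What is at stake is the protection of the individual subject at Tx 1. The intermediate safety report in section 8.3 uses data collected after Tx 1 and does not affect continuation, so it cannot serve this purpose.

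**Working it through.** The plan states no figure on this point to reproduce. The check compares its own time limits.

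**Inputs**
- Spot reading: 2 h or later (7.4.3).
- Tx 1: 0 to 7 days after Visit 0, that is 0 to 168 h (7.3.1, Appendix I).
- Excessive edema or erythema: unresolved at 2-3 days, that is 48 to 72 h (9.1.6).
- Applicator spot: 30 mm × 10 mm (6.1); up to three test spots (7.4.3).

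**Step 1. Gap at the earliest permitted start.** Definition time minus reading time: 48 − 2 = 46 h, and 72 − 2 = 70 h.

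**Step 2. Gap on any same-day start.** Such a start comes less than 24 h after the spot. The gap exceeds 48 − 24 = 24 h even at the lower limit of the definition. Waiting longer within the day does not close it.

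**Step 3. Which subjects can be affected.** The merged visit is not the only route. Because the chart puts the spots at Visit 1, a subject with separate Visits 0 and 1 can also have the spots and Tx 1 on one day. A subject gets a persistence reading only if the investigator chooses to place the spots 2-3 days ahead. The text allows that but does not ask for it.

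**Step 4. Exposure.** One spot is 3 cm × 1 cm = 3 cm²; three are 9 cm². Tx 1 covers the whole allocated area, whose size is not given.

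**Step 5. Whether a later reading fits.** With spots at Visit 0, the 168 h window leaves 168 − 48 = 120 h after the lower limit and 168 − 72 = 96 h after the upper. Tx 1 could fall on any of days 3 to 7, which is five possible days.

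**Step 6. What is observed after Tx 1.** Section 7.2.1.1 grades responses up to 30 minutes after treatment, and the next charted visit is "Tx #2 4-6 WKS POST Tx1". However, section 4.3 makes time to subside part of the safety endpoint, Table 1 has safety assessed throughout with subject interviews, and section 9.1 records any event that the subject reports. A persistent reaction can be captured, but only after full exposure.

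The number affected cannot be computed, because the documents give neither the share of same-day starts nor a rate of persistent reactions.

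**The case against.** The strongest reply is that the spot exists to choose settings and is not described as a screen for an event defined by duration. On that view the gap is true by definition for any reading before 48 h. Timing is left to clinical judgment: 2 hours is a floor, the investigator may wait up to a week, and treatment is not to start before the reaction is fully evaluated. Spots start at low fluence (5-10 J/cm² in Table 2, against 5-20 J/cm² available). Pain or an adverse event visible at the reading lowers the setting. Photosensitive subjects are excluded.

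All of this stands and limits the point. None of it shows persistence in the individual before Tx 1, and an investigator who starts 2 hours after the spot complies with the text.

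Two further objections also stand. Section 1.2 calls darker skin a greater challenge in connection with epidermal injury, so it gives no direct support for a concern about lingering edema or erythema. And the change proposed here covers the initial settings only; later increases, possibly to higher fluence, would stay on the 2-hour reading.

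A reader might infer that events after Tx 1 go unrecorded until the next visit. Section 4.3, Table 1 and section 9.1 show otherwise. A reader might also infer that burns, blistering or strong early reactions are missed. The documents do not support that: Table 2 acts on adverse events and pain seen at the spot, and the gap concerns only edema or erythema judged by duration.

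**Conclusion.** The point holds as a modest improvement in subject safety. The protocol permits, but does not require, full-area Tx 1 on the test-spot day. On such a start, one anticipated event cannot be recognised at the spot first, by 46 to 70 h at the minimum and by more than 24 h in every case. This rests only on reading 2-3 days as 48 to 72 h.

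It would go too far to say that the protocol contradicts itself. The spot's stated purpose is to choose settings, and no sentence promises that persistence will be excluded before Tx 1. Nor is any endpoint wrong, since the event stays reportable under section 9.1.6. The size of the benefit is unknown, and no estimate is offered. The change is worth considering because it fits the existing window at small cost.

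**What to change.** 1. **Appendix I and 7.3.1.** Place the initial test spots at Visit 0, after the baseline photographs and outside the hair-count window. Start adverse-event recording at Visit 0, since that row now begins at Visit 1. Set Visit 1 and Tx 1 at 3 to 7 days after Visit 0, delete the footnote that merges the visits, and replace the same-day allowance in 7.3.1 to match.
2. **7.4.3, reading.** Keep the 2-hour reading for stepping between spots. Re-read every spot at Visit 1 before Tx 1 and record the day on which any edema or erythema cleared. Do not use a setting whose spot still shows either, or any stronger setting (higher fluence, shorter pulse or more pulses).
3. **7.4.3, unresolved spots.** Report any spot reaction unresolved at 3 days as an anticipated adverse event under 9.1.6. If no tested setting has cleared at Visit 1, whichever day that is, defer Tx 1 until resolution and re-test at a lower setting. If none is available (already at 5 J/cm², 50 ms, one pulse), withdraw the subject.
4. **Safety report.** Include deferred and withdrawn subjects and their spot reactions. Section 5.1 replaces non-completers, so leaving out the most reactive subjects would lower the reported reaction rate.

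**Cost.** A protocol amendment and one CRF line. Subjects who would have merged Visits 0 and 1 need one extra attendance and wait 3 to 7 days. Those with separate visits need no extra attendance, but a Visit 1 planned before day 3 moves to day 3 or later. Any subject with no cleared setting is deferred and re-tested, or withdrawn. Later parameter changes remain on the 2-hour reading and are not screened for persistence.
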